6.3 Statistical criteria of termination of the investigation

If 6 or more patients show a postoperative hypersensitivity of FDI grade 4 or 5, the study will be terminated.

6.4 Planned Analyses

The IBM SPSS Version 25 software package will be used for data analysis.

6.4.1 Datasets to be analysed, analysis populations

The data collected of all eligible participants will be used for the statistical data analysis.

6.4.2 Primary Analysis

Regarding the primary outcome, the interim analysis will be done at baseline. The final analysis of the primary outcome will be done after 1 month. VAS values (biting and thermal stimuli) and the clinical signs and symptoms regarding tooth vitality, response to thermal tests, duration and intensity of pain are summarized in an FDI score as described by Hickel et al. (2022). It will be evaluated if the postoperative hypersensitivity rate (FDI criterium B3) is below 10% using a one-sided binomial exact test. Only FDI grades 3-5 will be considered as postoperative hypersensitivity, since FDI grade 2 does not need any treatment, subsides spontaneously, and does not have further clinical relevance. The analysis will be done by the principal investigator within 3 months after the collection of the data.

6.4.3 Secondary Analyses

Regarding the secondary outcomes, the analyses will be done after the 1, 6, 12, 24, 36 and 60 months recalls. A descriptive statistical analysis will be done by the principal investigator within 3 months after the collection of the data.

6.4.4 Interim analyses

The interim analysis will be done after the collection of data at each recall.

6.4.5 Deviation(s) from the original statistical plan

Deviations from the original statistical plan must be reported to the sponsor.

6.5 Handling of missing data and drop-outs

After baseline drop-outs will not be replaced. In previous clinical trials, there were few drop-outs in the internal clinic of Ivoclar Vivadent AG. There had also been a small number of no-shows.

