Inclusion / exclusion criteria:	
Inclusion criteria:
 
 • Informed Consent signed by the subject • Age: 18-65 years • Indication Class I or II direct restorations in premolars or molars (Replacement of insufficient fillings due to secondary caries, fractures, insufficient marginal adaptation, loss of filling or primary caries) • Cavity width must be at least half of the cusp tip distance • Vital teeth, regular sensitivity • Sufficient language skills • No active periodontitis • Preoperative VAS values < 3 regarding tooth sensitivity and biting 
Exclusion criteria:
 
 • Sufficient isolation of the cavity not possible • Not completed hygiene phase or poor oral hygiene • Missing antagonist, non-occlusion • Missing tooth adjacent to the tooth to be treated • Restorations replacing more than 1 cusp • Caries profunda or very deep cavity • Patients with a proven allergy to ingredients of the used materials (methacrylates) or local anesthetics (Articain, sulfite) • Patients with severe systemic diseases • Pregnancy • Part of the development project team of TM Flow or TM Fill • Staff of the study management team • Staff of the internal clinic
Measurements and procedures:	
Each participant receives one filling in one tooth. The fillings are assessed according to selected FDI criteria at baseline (7-10 days after filling placement) and after 1, 6, 12, 24, 36 and 60 months. At the 1 and 6 month recall the sensitivity is recorded using a visual analogue scale and at all the other recalls the sensitivity is only recorded if necessary. The results are documented by intraoral images.

Intervention:	
The newly developed resin composites TM Flow and TM Fill will be used for the restoration of class I and II cavities (3 seconds light-curing mode, 3000 mW/cm²). The treatment workflow is very similar to other resin composites, for instance the predecessor products Tetric PowerFill and Tetric PowerFlow.

Control intervention (if applicable):	
Not applicable

Number of subjects with rationale:	
61 subjects were calculated for the single-arm study design. Considering a drop-out rate of 5%, 65 subjects will be included in this clinical investigation.

Duration of the investigation:	
60 months for each patient (recruiting phase 4 months)

Investigation schedule:	
May 2024 First-subject-In April 2030 Last-subject-Out

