3. CLINICAL INVESTIGATION OUTCOMES

3.1 Primary Outcome

The primary outcome in this clinical trial is the FDI criteria - B3 pulpal hypersensitivity and pulpal status (Hickel et al. 2022) 1 month after placing of the fillings. FDI grades 3-5 are considered as postoperative hypersensitivity in this clinical investigation, since FDI grade 2 does not need any treatment, subsides spontaneously and does not have further clinical relevance. Postoperative hypersensitivity is considered an indicator of the response of a tooth (pulp) to the therapeutic procedure applied. Postoperative hypersensitivity can be observed within a short time after the treatment. Therefore, it is assessed for the first time at the baseline recall (after 7-10 days). The assessment of postoperative hypersensitivity includes questions about type and duration of pain, intensity of pain and on the stimulus inducing the pain. The subjective perception of the intensity of postoperative hypersensitivity caused by thermal stimuli and caused by occlusal forces (during biting) will be determined by the aid of a Visual Analog Scale (VAS). The VAS values are brought into relationship to the preoperative values. In the table below a description of the correlation between FDI grade and VAS values and clinical signs and symptoms is shown. Not all signs need to be present at one stage. The exact VAS values vary widely from patient to patient, depending on each individual's pain tolerance. Therefore, it is one of the factors influencing the FDI grade, but it is not directly correlated. Not all the described conditions have to be fulfilled to attribute an FDI score. Depending on the intensity and character of the pain, further therapy will be determined. Usually, postoperative hypersensitivity subsides spontaneously and no treatment is necessary. In case of very intense pain an immediate treatment is required. The application of a fluoride varnish is the first procedure of choice. If no improvement is achieved by this method, then the replacement of the restoration would be the next step. In the worst case, the pulp is severely inflamed, requiring endodontic treatment. If the postoperative hypersensitivity does not subside spontaneously or worsens after the applied treatment, the highest assessed FDI value is used for the statistical analysis.

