5 trained operators will insert 65 indirect restorations, so each operator will perform 13 restorations.

2 trained evaluators will perform the baseline examination (7-10 days) after placement of the restorations, and the following recalls at 1, 6, 12, 24, 36 and 60 months.

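### Section 6.5 bars replacement only after the 7-10 day recall, so by implication a participant lost between placement and that recall may be replaced and leave the primary rate

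*Combined protocol and SAP*

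**What the plan says.** The replacement rule is one sentence in Section 6.5: "After baseline drop-outs will not be replaced". The rest of that section notes few past drop-outs and no-shows at the internal clinic. It says nothing about losses before baseline or about a missing primary score.

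Baseline is a post-treatment visit throughout. Section 4.1 says "2 trained evaluators will perform the baseline examination (7-10 days) after placement of the restorations", and the synopsis (Measurements and procedures) gives the same window. In the Investigation Schedule the restoration is placed at Visit 1, day 0, and the 7-10 day recall is Visit 2. Adverse events are recorded from Visit 1.

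The primary outcome in Section 3.1 is FDI criterion B3 "1 month after placing of the fillings", with grades 3-5 counted as events. The same section says of hypersensitivity that "it is assessed for the first time at the baseline recall (after 7-10 days"). Where symptoms persist or get worse after treatment, it uses the highest grade assessed. Section 6.4.1 analyses the data of all eligible participants and does not define a treated set.

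**The concern.** A rule against replacement normally takes effect at exposure. Here it takes effect 7-10 days later, in a window that matters for this endpoint. Section 3.1 says "Postoperative hypersensitivity can be observed within a short time after the treatment", and also "In case of very intense pain an immediate treatment is required".

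A participant who leaves in that window has no scheduled B3 grade, so the highest-grade rule has nothing to work on. The adverse event record may show a painful tooth, but nothing carries it into the primary rate. Section 6.5 leaves open whether a new participant takes the place.

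If people leave because of pain, the analysed rate describes teeth that reached the first recall and not all teeth treated, and it moves towards passing. This is a pivotal, single-arm study for conformity assessment with a fixed 10% limit, so there is no comparator arm in which the same loss could offset it.

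**Working it through.** **Inputs from Sections 6.1 and 6.2.** P0 = 0.10, P1 = 0.024, one-sided exact binomial test at 0.05, n = 61 with 82% power, 5% drop-out, 65 enrolled.

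**Formula.** p-value for x events in n: P(X ≤ x) = Σ C(n,k)·0.10^k·0.90^(n−k), summed over k = 0 to x. Success requires p ≤ 0.05.

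**The plan's own figure.** At n = 61, P(X ≤ 2) = 0.0491 and P(X ≤ 3) = 0.129, so at most 2 events pass. Power at 0.024 is P(X ≤ 2) = 0.8195, which agrees with the stated 82%. 61/0.95 = 64.2, rounded up to 65. The design reproduces.

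**Effect of one case.**

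| Result analysed | p-value | Outcome |
|---|---|---|
| 3/65 | 0.0996 | fail |
| 2/65 (one event lost and replaced by a non-event) | 0.0360 | pass |
| 2/64 (one event lost, not replaced) | 0.0389 | pass |

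The result changes whether or not the lost participant is replaced. What matters is that the case leaves the count.

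**Illustration of size.** Suppose the true rate is 10% and a share f of would-be events leaves before the 7-10 day recall, while non-events do not leave. The documents give no value for f; the values below are assumptions. The event rate among those who remain is 0.10(1−f)/(1−0.10f).

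| f (assumed) | Rate among those remaining | False-pass probability, lost cases replaced (n = 65) | False-pass probability, lost cases dropped (65 treated) |
|---|---|---|---|
| 0 | 0.1000 | 0.036 | 0.036 |
| 10% | 0.0909 | 0.058 | 0.060 |
| 20% | 0.0816 | 0.092 | 0.098 |
| 30% | 0.0722 | 0.143 | 0.153 |

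The third column is P(X ≤ 2) at n = 65 with the reduced rate. The fourth averages over the number lost, which is binomial (65, 0.10f), using the critical value for the number left.

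**What the shares mean in people.** At a 10% rate, 65 × 0.10 = 6.5 events are expected. A 10% share is then 0.65 of a participant and a 30% share is 1.95. The whole 5% drop-out allowance is 65 × 0.05 = 3.25 participants.

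**The case against.** Several stronger readings are tempting, and the documents do not support them.

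- **That early losses will be replaced.** The text does not say so. Section 6.2 covers losses by enrolling 65 for 61 needed, and Section 4.1 fixes 65 restorations at 13 per operator; neither provides for extra placements. Replacement is permitted by implication only.
- **That replacement is itself the source of the bias, apart from missing data.** The table shows otherwise: dropping the same cases without replacement gives slightly higher false-pass probabilities.
- **That a participant with early pain is a likely event.** The FDI table in Section 3.1 puts symptoms under one week at grade 2, which is not an event, and over one week at grade 3. Section 3.1 also says that hypersensitivity usually subsides without treatment. Other signs can still lead to a higher grade, so early pain may or may not become an event.
- **That needing immediate treatment means leaving the study.** Section 3.1 describes treatment steps, and its table links them to grades. A participant who is treated and followed stays countable.
- **That the bias always runs towards passing.** It does so only if losses are related to pain. Other early losses, replaced or not, do not shift the expected rate.

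It is also fair to say that participants are company employees from the internal clinic's existing patients, with few past drop-outs. Losing two events within ten days, as the 30% row requires, would use more than half of the whole drop-out allowance.

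All of this limits the expected size. It does not close the gap: no section says what happens to a treated participant lost before the first recall, and the pass/fail result can turn on one such case.

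**Conclusion.** The point holds as an unspecified rule with a possible bias, not as a demonstrated one. The only replacement cut-off falls after exposure, and nothing in Sections 3.1, 6.4.1 or 6.5 keeps an early loss in the primary rate. If such losses are related to pain, the rate is biased towards the <10% criterion, and a single case can turn a fail into a pass.

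The size cannot be estimated from the documents. The false-pass probabilities of 5.8% to 14.3% rest on assumed shares of 10% to 30%, a true rate of 10%, and losses confined to events. With few early losses, or losses unrelated to pain, the effect would be small or nil. The change is still worth making before enrolment, because it costs little and the replacement rule and the missing-score rule have to be settled together.

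**What to change.** 1. **Section 6.5:** state that a participant may be replaced only if they leave before TM Flow/TM Fill is placed (Visit 1), and that nobody is replaced after placement.
2. **Section 6.4.1:** define the primary analysis set as all participants who received the restoration.
3. **Section 6.4.2 or 6.5:** count a B3 grade 3-5 documented at any contact after placement as an event if there is no later score.
4. **Sensitivity analysis:** count every treated participant with no B3 grade as an event, and report their number and reasons for loss.

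Item 1 alone would not be enough, as the 2/64 result shows. Item 3 helps only where a grade was recorded, so item 4 is needed for participants who leave unseen.

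The cost is a few sentences. There may be one or two fewer evaluable participants, which the margin from 61 to 65 covers: at n = 61 to 65 two events still pass. The observed rate may be slightly less favourable if an early case counted under item 3 would have resolved by 1 month.
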